**Proposal title: The Presence of Humanoid Robot with Older Adults at
Homes**

Date: 2022/01/13

Investigators

[name] (PI)

[name]

[name]

School of Nursing

The Hong Kong Polytechnic University

Background

Population ageing is rising rapidly across the globe. According to the Hong Kong Census and Statistics report, by 2021, one out of six Hong Kong people (15.7%) will be aged 65 or over.¹ This number will be doubled to 2.37 million (31.1%) in 2036.² According to the 2016 Hong Kong census³, about 150,000 adults aged 65 and above lived alone, and almost 300,000 lived with their older spouse. Older adults experience significant physical, cognitive and environmental losses in their later life. A recent survey in Hong Kong has shown that 75% of local adults aged 65 or over, and 45% of soon-to-be-aged people in the 45 to 64 age groups are suffering from one or more chronic diseases.⁴ Older adults are vulnerable to loneliness due to their health deterioration and age-related losses, which prevent them from participating in social activities and engaging in interpersonal relationships.⁵ Moreover, the experiences of loneliness can be worsened for older adults when they live alone or only with their spouses (who are also older adults). By 2040, the number of older people, who need support is expected to more than double, with the direct cost of this “ageing care” rising from HK\$38.8 billion (US\$5 billion) in 2018 to HK\$126 billion in 2040, and HK\$222.4 billion by 2060.⁶

In the field of gerontological nursing, person-centered holistic care highlights the importance of enabling older people and their significant others (such as older spouse or other family caregivers) to establish healthful relationships so to improve older adults’ physical, psychological, mental and social wellbeing⁷. Communications within the family and with friends is crucial for the ageing population and it has impacts on older adults’ psychological and mental health.⁸

Social robots are robotic technologies that are designed to interact autonomously with people, with a variety of application features, by using the same repertoire of social signals used by humans.⁹ Research on the use of robots addressing older adults’ loneliness is given increasing attention in the globe, but most of them were focused on aiding older adults who are living with dementia or residing in nursing homes,⁵ while very limited studies have been undertaken in Chinese population. Self-supported aging-in-place has positive benefits for social connection, social inclusion and the quality of life for older people¹⁰. Studies suggest that social robot and digital communication

technologies can contribute to the reduction of loneliness and social isolation in old age and such technology becomes a kind of social capital at their own homes.^{11 12} A recent study showed that older Chinese adults had high interests in having social robots during dining and entertainment in home-based aged care.¹³ Evidence showed that age, gender, education and computer experience on robot could impact on the acceptance of robot among older people.¹⁴ Another research in Hong Kong reported that individual attributes, such as gerontechnology self-efficacy and anxiety, health and ability characteristics, also affect the acceptance.¹⁵ However, more evidences are needed to examine the acceptance and feasibility of putting a social robot at home – investigation should be made to find out whether older adults, their spouses or other family caregivers at their homes accept, use and even live with these robots. Their experiences and perspectives on the use of the robots would be valuable to determine the use of technology in supporting ageing-in-place among older adults in the community.

Humanoid Robot 'HUMANE'

The humanoid robot is developed for integrating technology with human-like engagement, to support the wellbeing of older people and sustainability when aging-in-place by enriching an interactional environment, improving older adults' social and emotional engagement and delivering person-centered care. The robot has five main features:

1. Games and Quiz

The robot provides assessment and training in cognition. Quizzes and games are tailor-made according to different levels of cognitive abilities.

2. Personalized services – story telling, music playing, event reminder

[figure not shown]
The robot can tell stories, play music (according to older adults' preference) and remind older adults about date and time of the social events/health activities. Quizzes can be tailor-made by family members according to older adults' understanding and cognitive ability.

3. Socially connect to family members or friends: making phone calls

[figure not shown]
This feature provides connectivity services to reduce older people's social isolation and help foster connections with family, friends and community. The phone application

inside the robot connects the older adults with family members, relatives and friends, extending their social connections.

[figure not shown]
4. Promoting Healthy Lifestyle

The robot has an exercise system which encourages older people to exercise regularly. It will remind the older adults about daily health-related activities: drinking water, doing exercise and reading books.

Interactive modalities

The robot can talk, sing, play games, report weather and read the news. Older people can communicate with the robot via voice commands or a touch panel.

Aims of the study

This study aims to investigate the feasibility and acceptability of home-based physical robot HUMANE by community-dwelling Chinese older adults and soon-to-be-aged adults.

Objectives of the study

The objectives of the study are:

1. To investigate the feasibility of using different features of this robot HUMANE at home within 6 weeks;
2. To investigate the acceptability of the robot at home by older adults, their spouse, and other family members;
3. To assess the preliminary efficacy of this robot on loneliness, depression and mood and calculate the effect size of the use of the robot at home for a full RCT.

Methods

Study design

This study will employ a two-arm pilot randomized control trial with qualitative interviews.

Participants

The participants of this study are people aged 50 or above who are receiving home care from family members. Purposive sampling will be adopted in recruitment. We purposively look for people with different gender, age groups (20 people per each age

group: 50-60 years; 60-70 years; and 70-80 years), educational backgrounds and occupations, to reflect a diversity of views from the aged population. We will also recruit six computer ambassadors from a non-government organization in Hong Kong; these ambassadors have at least one-year experience in computer use. The ambassadors will be trained to support the study participants to use the robot during the intervention period.

As a pilot RCT study, a minimum sample size between 24 and 50 have been recommended.^{16 17} In this study, a total of **60 community-dwelling soon-to-be-aged or older adults** will be recruited. They would be randomized to two groups (intervention group, IG, and control group, CG), that is, 30 adults will be randomized to IG while the other 30 adults will be assigned to CG. Thirty family caregivers will also be recruited through participants assigned in IG group.

The inclusion criteria

1.1 For community-dwelling soon-to-be-aged or older adults

- Ethnic Chinese aged 50 years and above;
- Need home-based care from family caregiver, including spouses;
- Live with at least one family caregiver at his/her own home (not in residential care homes) in Hong Kong;
- Are able to communicate in Cantonese or Putonghua.

1.2 For family caregivers

- Live with the participating older adult in the same household or in other household but with regular contacts (at least once per week) with the participating older adults
- Are able to communicate in Cantonese or Putonghua

The exclusion criterion for the participants are those:

- With acute mental disorders or disabling diseases that may limit the practice of engaging with robot; and
- have limited access to electricity and this makes them hard to use technology at home.

Intervention

The robot HUMANE will be used by the IG (30 participants) for an 6-week trial. Project team will set up a physical robot at their homes. Each participant will be given a protocol to engage with different features of the robot every day. Participants are asked to complete the assigned daily tasks at their own homes. **Table 1** shows the 6-week tasks with the robot HUMANE.

Phone counselling will be given to support the study participants by the trained ambassadors. A training workshop will be given to the ambassadors by the technical team before the intervention starts. A hotline will be set up for the participants and volunteers during the trial period to provide technical support. Participants will be encouraged to contact the ambassadors if they need support and when they had completed daily tasks. The ambassadors will contact the assigned participants (one ambassadors will be assigned with 5 participants) every three days by phone to ensure continued participation and to follow up on their progress.

Table 1. 6-week tasks of engaging with the robot HUMANE

Days	Tasks
Week 1	
• Set up the robot• Complete the baseline assessment[#]
Week 2	
• Explore the features of the robot with the caregiver• Talk to the robot
Week 3	
• Communicate with two relatives using the robot• Record the appointments in the next 2 months
Week 4	
• Check the calendar, weather forecast and read news• Search and listen music with the robot• Do 30-minute exercises with the robot
Week 5	
• Check the calendar, weather forecast and read news• Play games with the caregiver on the robot• Communicate with a friend using the robot• Perform a task according to the calendar• Play cognitive training games with the robot
Week 6	
• Check the calendar, weather forecast and read news• Share at least one interesting news to the caregiver• Play cognitive training games with the robot

[#]Assessment: 6-item Chinese De Jong Gierveld loneliness scale, the Chinese version of the 2Q questionnaire, The Chinese version of the General Self-Efficacy Scale, the Chinese version of the social capital scale, the Chinese version of mutuality scale and the 5-item Abbreviated Memory Inventory for the Chinese (AMIC)

Outcome measures of feasibility and acceptability study

The measures in the feasibility and acceptability study include: 1) recruitment rate of participants, 2) completion rate of the assigned tasks, 3) retention rate of the participants and 4) experiences for using the robot.

Quantitative method

Demographic data will be collected at baseline before intervention. Upon completing each session, login frequency and durations of engaging each feature of robots will be collected and counted via the robotic management system to examine home care receivers' compliance of engaging the robot HUMANE and preferences of specific features. 'Video capture' function of the HUMANE will be utilized to capture the situation when a home care receiver is using the robot on some time slots. The usability of robot will be assessed by the Chinese version of the system usability scale (SUS)¹⁸ upon the completion of the intervention. The System Usability Scale (SUS) is a widely used instrument that measures the subjective usability of products and systems. The Chinese SUS has been tested and showed to be reliable, effective and sensitive. The scale contains 10 questions based on the Likert five-point scale; questions 1, 3, 5, 7, and 9 are positive and questions 2, 4, 6, 8, and 10 are negative. The 10 questions are closely related and are employed for the comprehensive evaluation of a product. A higher SUS score indicates better product usability.

Qualitative method

The perspectives and experience of using home-based robot HUMANE will be collected from home care receivers and their family caregivers through a 30mins in-depth individual interview. The questions that will be asked are framed with reference to the guideline on feasibility studies for intervention trials¹⁹. The guiding questions are as follows: 1) Acceptability: what do you think about the acceptability or satisfaction of using the robot at home? 2) Integration: what do you think if the robot can be integrated into the normal routine of your life? 3) Practicality: what are the practical concern regarding the robot? 4) Efficacy: what changes do you have after you have engaged with the robot (for family caregiver: what changes do you observe the family member have after engaged with the robot)? The interview will be ceased until research team were satisfied that thematic saturation²⁰ was reached.

Recruitment Rate

Research assistant will maintain a detailed record of the total number of target population accessed, recruited and retained. The study costs, human resources, the time taken for recruitment, the number of contacts, visits, the challenges encountered, reasons for withdrawal from the study, and factors that influenced recruitment and study completion rates will be recorded accordingly.

Outcome measures in pilot RCT

The following outcomes will be measured: 1) loneliness, 2) cognitive function, 3) emotional status, 4) self-efficacy, 5) social capital and 6) mutuality. The measurements will be utilized at baseline (day-1) and immediately post-intervention (week-6) to examine preliminary effect of using robot at home.

Loneliness

The loneliness status of participants will be explored to inform the selection of outcome measures in a full RCT to assess the effectiveness of the intervention. The 6-item Chinese de Jong Gierveld Loneliness Scale ²¹ consists of emotional loneliness and social loneliness two subscales, each of them contains three items. They are three response categories for each item: “no”, “more or less”, and “yes.” The scale has been validated and recommended as a reliable (Cronbach’s α of the 6-item scale was 0.76, the intra-class correlation coefficients ranged from 0.98 to 1.00) and valid (the content validity was high as shown by the results of the Delphi panel) measure of loneliness in older Chinese ²¹.

Cognitive function

In this study, a 5-item Abbreviated Memory Inventory for the Chinese (AMIC) 16 will be used to assess participants’ cognitive function. AMIC is an abbreviated version of the original 27-item Memory Inventory for Chinese people, with a sensitivity of 54.6%-65.3% and specificity of 57.4%. There are five items: “Do you always forget where you put your stuff?”, “Do you feel that your memory is worse than your peers?”, “Do you always forget what you want to say during a conversation?”, “Do you always fail to find the appropriate word to express your idea during a conversation?”, and “Do you forget your acquaintances’ names when you meet them?”. AMIC scores range from 0-5 (1 point for each item; 0-best to 5-worse). An AMIC score ≥ 3 is predictive of MCI.

Emotion status

The Chinese version of 2Q questionnaire was chosen because of the high sensitivity and that it was simple to use²². The 2Q was derived from the Primary Care Evaluation of Mental Disorders Procedure (PRIME-MD). The questionnaire includes two questions about depressed mood and anhedonia: "During the past month, have you often been bothered by feeling down, depressed, or hopeless?" and "During the past month, have you often been bothered by little interest or pleasure in doing things?" It is recommended a useful measure for screening depression in primary care in Hong Kong²².

Self-efficacy

The Chinese version of the General Self-Efficacy Scale is a reliable and valid scale that can be used with confidence in community Chinese soon-to-be-aged adults²³. The CGSE Scale consists of 10 items that measure a generalized sense of competence. All items are rated on a 4-point Likert scale ranging from 1='Not at all true' to 4='Exactly true'. The higher the score, the greater self-efficacy the respondents possess.

Social capital

Social capital will be evaluated using the social capital scale to cover the two dimensions of social capital (social cohesion and social interaction) developed by Mujahid ²⁴. The social cohesion subscale consists of 4 items: 1) People around here are willing to help their neighbors, 2) People in my neighborhood generally get along with each other, 3) People in my neighborhood can be trusted, 4) People in my neighborhood share the same values. Each item ranged from 1 to 5 (1 = strongly disagree, 2 = disagree, 3 = neutral, 4 = agree, and 5 = strongly agree). Cronbach's alpha was 0.81 among the Chinese community-dwelling older adults²⁵.

Mutuality

Mutuality was assessed with the Chinese version of the Mutuality Scale, which consisted of questions related to love, shared activities, values, and reciprocity ²⁶. Each item was rated with a 5-point Likert scale ranging from 0 ("not at all") to 4 ("a great deal"); the total score was the mean of all items (ranging from 0 to 4). Higher scores implied greater

mutuality. Cronbach's alpha was 0.96 for dementia patients and 0.94 for caregivers respectively²⁶.

Data analysis

SPSS Statistics 26 will be adopted for all analyses. Descriptive statistics will be used to summarize the participant characteristics. Differences between the intervention and control groups in relation to outcome measures will be compared across multiple time points using generalized estimating equations (GEE) models or generalized linear mixed model (GLMM). The effect size will be computed to show the magnitude and direction of the effect of the intervention group relative to the control condition for each outcome variable. The usage statistics will be calculated and used to reflect the feasibility of the intervention. A deductive content analysis approach will be used to analyze the transcribed interview verbatim in relation to the feasibility of the intervention, which is considered suitable for a detailed analysis of the four indicators of the feasibility of the intervention: acceptability, integration, practicality, and efficacy¹⁹.

Ethical and safety considerations

Ethics approval and permission will be obtained from the study university before study undertaken. The research participants' privacy, safety, health, social sensitivities, and welfare will be adequately protected according to the university ethics' requirements. There will be no serious risks anticipated for this research. The surveys and interviews were not designed to place participants in an uncomfortable position. Researchers will provide participants with contact details for the study if they have any concerns.

Before enrolment into this study, all participants will give written informed consent and they will be free to refuse to any assessments and withdraw from the study at any time. All study documents will be stored in a locked filing cabinet at the study university. Only the project team members have access to the consent forms. All study relevant data will be permanently deleted by the primary researcher after 7 years. Confidentiality will be maintained through replacing all names of individuals with pseudonyms and changing any potentially identifiable details in the transcripts and any reports, presentations, or publications arising from the research.

Study timeline

month	1	2	3	4	5	6	7	8	9	10	11	12
Recruit research staff	x											
IRB submission and approval	x											
Recruit 60 participants	x											
Training for 6 ambassadors	x	x										
6-week trial for using the robot (1-10 participants)			x	x	x							
6-week trial for using the robot (11-20 participants)					x	x	x					
6-week trial for using the robot (21-30 participants)							x	x	x			
Baseline assessment			x		x		x					
Post-intervention assessment					x		x		x			
Qualitative interviews			x	x	x	x	x	x				
Data analysis				x	x	x	x	x	x	x	x	
Report preparation and results dissemination										x	x	x

Reference

1. Census and Statistics Department. Population by Sex and Age Group 2021 [Available from: https://www.censtatd.gov.hk/en/web_table.html?id=1A accessed 30 October 2021.
2. Census and Statistic Department. Population Projections Census and Statistic Department Web site2017 [Available from: <https://www.censtatd.gov.hk/en/EIndexbySubject.html?PCODE=FA100061&SCODE=190> accessed 30 October 2021.
3. Census and Statistic Department. Domestic Households in Hong Kong. Retrieved from HKSAR Census and Statistic Department Web site2016 [Available from: <https://www.bycensus2016.gov.hk/en/Snapshot-04.html> accessed 30 October 2021.
4. Elderly Commission. Report on Healthy Ageing Executive Summary 2021 [Available from: <https://www.elderlycommission.gov.hk/en/library/Ex-sum.htm> accessed 23 Nov 2021.
5. Gasteiger N, et al. Older adults' experiences and perceptions of living with Bomy, an assistive dailycare robot: a qualitative study. *Assistive Technology* 2021 doi: 10.1080/10400435.2021.1877210

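### The outcome baseline is a Week 1 task of the robot arm and is never placed before randomisation, so robot-arm baselines would probably be given with the allocation known

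*Protocol*

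**What the plan says.** Four parts of the protocol bear on when the outcome baseline is taken.

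- **Intervention and Table 1.** The section opens with "The robot HUMANE will be used by the IG (30 participants) for an 6-week trial", so Table 1 is the robot arm's task list. Week 1 has two items: setting up the robot, and "Complete the baseline assessment". The footnote to the table lists six instruments: loneliness, 2Q, self-efficacy, social capital, mutuality and AMIC.
- **Participants.** Of the 60 participants, "They would be randomized to two groups (intervention group, IG, and control group, CG"), 30 to each. No date or study day is given for this step. Family caregivers are recruited through participants already assigned to the robot arm.
- **Outcome measures.** Under Quantitative method, "Demographic data will be collected at baseline before intervention"; this sentence covers demographics only. Under Outcome measures in pilot RCT, "The measurements will be utilized at baseline (day-1) and immediately post-intervention (week-6"). Neither sentence mentions randomisation.
- **Study timeline.** "Recruit 60 participants" is marked in month 1. The robot batches (participants 1-10, 11-20 and 21-30) start in months 3, 5 and 7. Baseline assessment is marked in months 3, 5 and 7. There is no row for randomisation.

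Under Data analysis, differences between the groups "will be compared across multiple time points using generalized estimating equations (GEE) models" or a GLMM. Objective 3 uses the result to "calculate the effect size of the use of the robot at home for a full RCT".

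**The concern.** A participant working through Table 1 has been assigned a robot. If the baseline scales are one of that participant's tasks, they are answered after allocation. The scales are self-reported, and a robot in the home cannot be hidden from the person answering. Knowing the arm could change how people rate their loneliness, mood or self-efficacy, and at baseline it could do so in one arm differently from the other.

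Randomisation makes the arms comparable at baseline, apart from chance, only for what is measured before the allocation is known. A baseline taken afterwards loses that property, and the data cannot separate a shift caused by knowing the arm from a chance imbalance. The planned comparison over time uses this baseline, so an error there passes into the effect sizes meant for the full trial.

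**Working it through.** The protocol gives no figure to reproduce here. The check sets its statements on timing side by side.

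1. **What is assessed.** The Table 1 footnote names 6 scales. Outcome measures in pilot RCT lists 6 outcomes, and they correspond one to one. The Week 1 assessment is therefore the outcome baseline, not a separate questionnaire.
2. **Who does it under Table 1.** The robot batches in the timeline total 10 + 10 + 10 = 30, the size of the robot arm. Table 1 and the batches describe the same 30 people, all identified as robot users.
3. **When it happens.** Baseline months {3, 5, 7} equal the batch start months {3, 5, 7}. Recruitment is in month 1, so the gaps from recruitment to baseline are 3 - 1 = 2, 5 - 1 = 4 and 7 - 1 = 6 months. Baseline follows the start of each robot batch, not recruitment.
4. **Whether any statement puts it before allocation.** Randomisation has no date under Participants and no row in the timeline. The statement about data collected before the intervention covers demographics only. The day-1 label can be read as the first day or as the day before; neither reading places it before allocation.
5. **When controls are assessed.** The baseline and post-intervention rows of the timeline are not restricted to the robot arm, but no sentence says in which months controls complete the scales.

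**Effect on the analysis.** Let knowledge of the arm shift robot-arm answers relative to control by b at baseline and by f at week 6.

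- Expected group-by-time contrast = true effect + f - b.
- With baseline before randomisation, b = 0 by design, and the contrast is true effect + f.
- If b = f, the shifts cancel in the contrast as now planned.

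The protocol gives no value for b, f or the true effect, so the algebra shows how the error enters but not how large it is.

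**The case against.** The order is inferred. The protocol never dates randomisation, and a sequence of consent, day-1 scales, allocation and then set-up at each batch start is not excluded. This stands, and it is why the point says *probably*. It does not remove the problem: a task listed for robot users presupposes that they are robot users, and no other statement corrects Table 1.

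A reader might infer that the robot is already installed, or even in use, when the scales are completed. The documents do not support that. The two Week 1 items are unordered bullets, exploring and talking to the robot are listed from Week 2, and the day-1 label may mean the day before. The supported concern is knowledge of the arm.

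It is also fair that the scales may not be equally open to a shift. The 2Q asks about the past month, and the social cohesion items ask about neighbours. For some scales b may be close to zero.

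A further objection is that the change need not bring the estimate closer to the truth: with b = f the present contrast is unbiased, and setting b to zero leaves f. This too is correct. The gain is a baseline that is comparable by design, not a guaranteed smaller error.

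Finally, the main aim is feasibility and acceptability, and the effect sizes are called preliminary. That limits the weight of the point. It is still not a matter to leave to an analysis plan, because no analysis can turn a baseline taken after allocation into one taken before it.

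**Conclusion.** The point holds as a probable flaw in the order of procedures, not as a stated one. Table 1 and the timeline both tie the six-scale baseline to the start of robot use, and nothing places it before randomisation. Followed as written, robot-arm baselines would probably be given with the allocation known.

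The consequence is a possible bias in the objective 3 effect sizes, of unknown size and direction. A reader might want a range in standard deviations, but any such range would rest wholly on assumed shifts, so none is given. Feasibility and acceptability results are not affected. Expectation effects at week 6 remain whatever is done about baseline. Nor can one infer that controls have no baseline: the outcome section and the timeline rows are not limited to one arm, and only the months for controls are left unstated.

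The conclusion rests on two readings: that Table 1 applies to the robot arm only, and that the timeline marks fall in the months read here.

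**What to change.** 1. Remove the baseline assessment from Week 1 of Table 1.
2. State under Outcome measures in pilot RCT that in both arms all six scales are completed after consent and before randomisation and robot set-up, and define day-1 to match.
3. Keep baseline in months 3, 5 and 7. Assess each batch and then randomise it just before it starts. With 60 participants in three batches, each has 60 / 3 = 20 people, 10 robot and 10 control.
4. State that controls are assessed at baseline and week 6 in the same months as the robot users of their batch, and add randomisation to the timeline.

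One early baseline before a single randomisation in month 1 would also precede allocation, but it would leave gaps of 2, 4 and 6 months before the batches start and would conflict with a day-1 baseline. Batch-wise randomisation avoids this.

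**Cost.** No extra participants or assessments are needed, only edits to Table 1, the outcome section and the timeline. The real price is that allocation, and the recruitment of caregivers through the robot arm, come later for batches 2 and 3 than if everyone were allocated at recruitment.

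### The robot logs are read as both compliance and feature preference, but Table 1 assigns features for unequal numbers of weeks, so comparing overall logged use mixes assignment with preference

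*Protocol*

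**What the plan says.** Under Outcome measures of feasibility and acceptability study, the Quantitative method paragraph states that "login frequency and durations of engaging each feature of robots will be collected and counted via the robotic management system". These data are to examine care receivers' "compliance of engaging the robot HUMANE and preferences of specific features". One set of logs thus serves both readings.

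Use over the six weeks is directed. The Intervention section says "Participants are asked to complete the assigned daily tasks at their own homes", and the ambassadors contact their participants "every three days by phone to ensure continued participation and to follow up on their progress". Table 1 sets the tasks week by week. "Check the calendar, weather forecast and read news" appears in Weeks 4, 5 and 6, while "Search and listen music with the robot" and "Do 30-minute exercises with the robot" appear in Week 4 only. The robot's description lists story telling among its personalised services, but Table 1 does not name it. Week 2 has a general task of exploring the features with the caregiver.

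The Data analysis section says that usage statistics will be used to reflect feasibility. It does not separate assigned from voluntary use. Objective 1 is "To investigate the feasibility of using different features of this robot HUMANE at home within 6 weeks".

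**The concern.** A session logged because a task was set, with a follow-up call due, is evidence of compliance. A session logged when nothing was asked is evidence of preference. A per-feature count that pools the two cannot be read as either one. If participants simply do what Table 1 asks, features assigned in more weeks show more use even when nobody prefers them.

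At stake is the feature-level part of Objective 1: frequently assigned features could look liked, and a feature with no named task could look unwanted. The other instruments do not fill the gap. The System Usability Scale rates the product as a whole. The four guiding questions under Qualitative method cover acceptability, integration, practicality and efficacy of the robot, and none asks which feature a participant prefers.

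**Working it through.** The protocol gives no figure to reproduce. The check is a count from Table 1, followed by two illustrations on stated assumptions.

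**1. Assigned and unassigned weeks.** Week 1 is set-up and baseline, so Weeks 2 to 6 (five weeks) are counted.

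| Feature | Weeks named | Number | Unassigned weeks before first assignment | Unassigned weeks after |
|---|---|---|---|---|
| Calendar, weather, news | 4, 5, 6 | 3 | 2, 3 | none |
| Cognitive training games | 5, 6 | 2 | 2, 3, 4 | none |
| Calls | 3, 5 | 2 | 2 | 4, 6 |
| Talking to the robot | 2 | 1 | none | 3, 4, 5, 6 |
| Music | 4 | 1 | 2, 3 | 5, 6 |
| Exercise | 4 | 1 | 2, 3 | 5, 6 |
| Story telling | none by name | 0 | not applicable | not applicable |

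The imbalance is, if anything, understated. Recording appointments (Week 3) and carrying out a calendar task (Week 5) add further calendar use, and sharing a news item (Week 6) adds news use.

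**2. No preference at all.** Assume every participant logs *r* sessions of a feature in a week that names it and 1 session in any other week. With *a* assigned weeks, the total is *r* × *a* + (5 − *a*).

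- *r* = 3: news 3×3 + 2 = 11; cognitive games and calls 3×2 + 3 = 9; music and exercise 3×1 + 4 = 7; story telling 5. Largest to smallest: 11/5 = 2.2.
- *r* = 5: news 5×3 + 2 = 17; cognitive games and calls 5×2 + 3 = 13; music and exercise 5×1 + 4 = 9; story telling 5. Largest to smallest: 17/5 = 3.4.

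The session rates are assumptions. The spread comes only from Table 1.

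**3. With real preferences.** This simulation takes the seven features above, with games treated as one feature assigned in Weeks 5 and 6, and 30 participants. The assigned feature-weeks are 3 + 2 + 2 + 1 + 1 + 1 + 0 = 10. The expected log for feature *j* is 30 × (*s* × *a_j* + *F* × *p_j*), where:

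- *s* is 7 or 1 assigned sessions per assigned week;
- *p_j* is a randomly drawn preference share (flat Dirichlet);
- *F* = 10*s* × *u*/(1 − *u*), with *u* the share of all use that is unassigned.

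Counts are Poisson, with 3,000 draws per setting. The table gives mean Spearman correlations of logged use; where two values appear, they are for *s* = 7 and *s* = 1.

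| Unassigned share *u* | With assigned weeks | With true preference |
|---|---|---|
| 0% | 0.95 | about 0 |
| 10% | 0.95 | 0.14 / 0.10 |
| 25% | 0.90 / 0.88 | 0.28 / 0.27 |
| 50% | 0.60 / 0.59 | 0.66 / 0.65 |
| 75% | 0.26 | 0.89 |

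Up to about 25% unassigned use, the logs mainly show the assignment. At 50% the two influences are about equal, and at 75% preference dominates.

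**4. Duration.** Using duration instead of frequency does not remove the problem, because the exercise task itself sets a length of 30 minutes.

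**The case against.** The strongest reply is that the protocol announces neither a ranking of features nor a six-week total. Data are logged after each session, so a week-by-week summary remains possible, and such summaries are usually left to the analysis plan. Preference is not one of the four listed feasibility measures or the three objectives, and completion of assigned tasks has its own measure. Voluntary use is nowhere forbidden. Participants also receive a daily protocol that may be fuller than the weekly list in Table 1.

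Much of this stands, and it limits the point. A reader might infer three stronger things that the documents do not support:

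- **That logged preference would largely reproduce the assignment.** This depends on the share of unassigned use, which is not given.
- **That quizzes and the water or reading reminders are also unassigned features.** Quizzes share a heading with games, which are assigned, and the reminders are started by the robot rather than chosen by the user. Story telling itself is one item under a wider heading that includes music and event reminders, and the Week 2 exploration may reach it.
- **That features will be kept or dropped for the full trial on these counts.** The protocol states no such decision.

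Deferral to the analysis plan does not answer the core point. The protocol itself fixes both the schedule of assignment and the inference to be drawn from the logs. No later analysis can recover voluntary use after introduction for features assigned through to Week 6.

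**Conclusion.** The point holds as a confounding of preference with assignment in any comparison of features on overall logged use. The unequal assignment (three weeks down to none by name) is a matter of record in Table 1. The size of the distortion is not known. The 2.2-fold to 3.4-fold spread under no preference rests on the assumed session rates. The threshold of about 25% unassigned use rests on the simulation's assumptions about preferences and session counts. The consequence is modest, because preference is a secondary, descriptive reading in a pilot; recruitment, task completion and retention are not affected. It is worth correcting because the change is cheap and no other instrument asks about preference between features.

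**What to change.** In the Quantitative method paragraph, split the use of the logs:

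1. **Compliance:** use of a feature in the weeks in which Table 1 assigns it.
2. **Preference:** use only in weeks when the feature is not assigned, reported per week and separately for weeks before and after its first assignment. This keeps order and novelty visible. Show Week 2 as the common exploration period, noting that talking to the robot is assigned in that week.
3. State that features will not be compared on total six-week frequency or duration.
4. State that for calendar, weather and news, and for cognitive games, voluntary use after introduction cannot be separated from assignment because both are assigned through Week 6.
5. Add one question on feature preference to the interview guide under Qualitative method. The four existing questions do not supply it.

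Table 1 and the data collected by the robot system need not change. The cost is some wording, a week-by-week tabulation and one interview question. The downside is that fewer logged weeks inform preference, and the two features assigned through Week 6 cannot be compared on the logs after their introduction.
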